#### **6.5 Sample Size and Power**

Our primary endpoint is the change in sputum %PMNs pre- and 4 hours post-WSP exposure, comparing prednisone to placebo. This study originally targeted enrollment of 24 subjects to yield complete 20 datasets, enrolled a total of 7 subjects and completed 6 prior to the study being put on hold for the pandemic from March 2020 till July 2021. No samples had been analyzed from this study yet. Meanwhile our ongoing WSP screen protocol was able to complete 50 screening exposures, determining that 28 met the predefined “responder” definition. These samples were collected pre-pandemic and were processed during the pandemic pause, yielding results that the responder group has a mean baseline of 24% PMN which increases to 40% at 6 hrs and 52% 24 hrs post exposure. The availability of these new data have led to concern that the Smokisone enrollment target should be amended, since the new dataset should allow a more accurate sample estimate. Using our ongoing WSP screen sputum data, estimating the prednisone effect size to be a 50% inhibition of WSP-induced sputum neutrophilia based on a previously published study of prednisone effect on sputum neutrophilia after controlled ozone exposure [2], and assuming a more conservative standard deviation for the prednisone effect size than the one reported in that study, we estimate that the N for this study to detect a significant prednisone effect should be 12 rather than 20. Anticipating 5-10% of subjects will produce inadequate samples, we propose a goal of completing 14 subjects to obtain 12 complete datasets.

## 6.6 Interim Analysis

We do not plan on conducting an interim analysis. Prednisone dosing is being used for its indication as an anti-inflammatory treatment. Because we do not anticipate safety concerns attributable to prednisone treatment for 1 dose, no interim analysis will be needed. Additionally, our study will be reviewed and surveyed by the Data and Safety Monitoring Board for external safety monitoring.

## 7 STUDY INTERVENTION

- **Description**  
Prednisone 60 mg (supplied as three Prednisone 20 mg tablets USP)
- **Receipt/Storage**  
IDS will be responsible for providing prednisone and matching placebo for each study subject and for each treatment period in a blinded fashion.
- **Packaging/Labeling**  
This is a randomized, double blind study so packaging and labeling by IDS is such that both study participants and study personnel will be blinded to the treatment (either prednisone or placebo) given.
- **Dosing**  
Study participants will receive 60 mg of prednisone (3 tablets of prednisone 20 mg) or matching placebo during period 1. They will then crossover to period 2 and receive the alternative treatment. Prednisone 60 mg is the standard clinical daily dose used to treat exacerbations of airway diseases, such as asthma and COPD.
- **Treatment compliance and Adherence**  
Subjects are observed during all dosing periods.
- **Drug Return/Destruction:** n/a
- **Drug Accountability:** n/a

## 8 STUDY INTERVENTION ADMINISTRATION

- **Randomization procedures**  
The randomization schedule will be generated by one of [name] colleagues using permuted block randomization with a block size of 4 (2 prednisone, 2 placebo) for the first treatment period of the protocol).
- **Blinding procedures**

- This is a randomized, double blind study so packaging and labeling by IDS is such that both study participants and study personnel (coordinators and physicians) will be blinded to the treatment (either prednisone or placebo) given.
- **Unblinding procedures:** Unblinding will occur at the conclusion of the study or earlier if needed for safety purposes and as dictated by the UNC IRB, study sponsor, and DSMB.

## 9 SAFETY MANAGEMENT

- **Definition of Adverse Event (AE) and Serious Adverse Event (SAE)**  
An AE for a given volunteer will be defined as failure of any of the safety criteria outlined above. Any symptoms that induce a volunteer to seek medical attention from any provider within 96 hours of a study visit will also be considered an AE. A SAE will be defined as any event that requires hospitalization or results in life threatening illness or injury, permanent (or likely to be permanent) illness or injury, or death if these events occur within 96 hours of a study visit (or if the clinical scenario leading up to hospitalization, illness, injury or death begins within 96 hours of a study treatment visit).
- **Grading criteria**
  - In addition to determining whether an adverse event fulfills criteria for a SAE or not, the severity of AEs experienced by study participants will be graded according to the criteria set forth in the National Cancer Institute's Common Terminology Criteria for Adverse Events (NCI-CTCAE) Version 4.0. This document provides a common language to describe levels of severity, to analyze and interpret data, and to articulate the clinical significance of all adverse events.
  - All adverse events whether or not listed in the NCI-CTCAE will be graded on a scale from 1 to 5 according to the following standards in the NCI-CTCAE manual (A semi-colon indicates 'or' within the description of the grade.):
    - Grade 1 = Mild; asymptomatic or mild symptoms; clinical or diagnostic observations only; intervention not indicated.
    - Grade 2 = Moderate; minimal, local or noninvasive intervention indicated; limiting age-appropriate instrumental activities of daily living (ADL) (preparing meals, shopping for groceries or clothes, using the telephone, managing money, etc).
    - Grade 3 = Severe or medically significant but not immediately life-threatening; hospitalization or prolongation of hospitalization indicated; disabling; limiting self-care ADL (bathing, dressing and undressing, feeding self, using the toilet, taking medications, and not bedridden).
    - Grade 4 = Life-threatening consequences; or urgent intervention indicated.
    - Grade 5 = Death related to AE.
- **Adverse Event/Serious Adverse Event monitoring procedures**  
Evaluations for safety throughout study visits are detailed in Section 5.3. In addition to these, review and classification of AEs will occur at each study visit with ongoing monitoring of safety throughout the entirety of the study by the PI. The UNC DSMB will be employed to review AEs throughout the study. The PI will report to the DSMA at least biannually. Any SAE;s will be immediately reported to the DSMB.

- **Adverse Event/Serious Adverse Event reporting procedures**  
All SAEs will be reported to UNC IRB, DSMB, and funding agency within 24-48 hours, and all AEs will be reported to UNC IRB and DSMB at regular predetermined intervals per protocol. Per DoD guidelines, only the following events will be reported to the HRPO: (1) All unanticipated problems involving risk to subjects or others; (2) Suspensions, clinical holds (voluntary or involuntary), or terminations of this research by the IRB, the institution, the sponsor, or regulatory agencies; (3) Any instances of serious or continuing noncompliance with the federal regulations or IRB requirements; (4) The knowledge of any pending compliance inspection/visit by the Food and Drug Administration (FDA), Office for Human Research Protections, or other government agency concerning this clinical investigation or research; (5) The issuance of inspection reports, FDA Form 483, warning letters, or actions taken by any government regulatory agencies; (6) Change in subject status when a previously enrolled human subject becomes a prisoner must be promptly reported to the USAMRMC ORP HRPO with a report that includes actions taken by the institution and the IRB. The duties of the RM specifically will be to review all unanticipated problems involving risks to subjects or others associated with the protocol and provide an independent report of the event to the IRB and DSMB. The PI will stop a research protocol in progress, remove individual human subjects from a research protocol, and will protect the safety and well-being of human subjects until the IRB and DSMB can assess the report. All findings from these events will be promptly reported to the HRPO.
- **Medical Emergency procedures**  
There is a study physician available for study visits, including WSP exposure. A code cart and Automated External Defibrillator (AED) are available in the event of a cardiopulmonary event. Albuterol, both inhalers and nebulizers, are available in the event of bronchospasm. If a subject has an event that does not immediately respond to care in the research lab, he/she will be transported via EMS to UNC Healthcare for treatment.
- **Data Safety Monitoring Plan**  
Data is initially recorded on paper documents, and the documents are maintained in a binder, which is kept in a locked office within the EPA Human Studies Facility (HSF). The EPA HSF is a secure facility with a guarded entrance and requires identification for entry. This data is then entered into REDCap by an initial data entry person, and confirmed by a second user.
- **Potential Risks:**
  - a) **WSP exposure:** Concentrations of wood smoke exhaust proposed for this study ( $500 \mu\text{g}/\text{m}^3$ ) are below those reported for individuals using biomass burning for heating and food preparation and those living in the area of a forest fire or agricultural burning. No major adverse health effects were observed in a recently completed study, which exposed healthy volunteers to WSP (21). The mean PM was  $485 + 84 \mu\text{g}/\text{m}^3$  during the WSP exposure (vs. "below the detectable limit" for filtered air (FA)), and analyses of chamber concentrations of total hydrocarbon and carbon monoxide during WSP exposure were also increased compared to FA ( $4.8 \pm 0.5$  vs.  $2.0 \pm 0.1$  ppm and  $2.7 \pm 0.7$  vs.  $0.0 \pm 0.0$  ppm, respectively). However, these healthy subjects had no significant

change in pulmonary function and no nasal irritation, rhinitis, inspiratory pain, shortness of breath, cough, wheezing or chest tightness after exposure to WSP or filtered air. There were complaints of fatigue, headache and eye irritation, but these were noted by volunteers as frequently before as after both the filtered air and particle exposures. Pulmonary function testing demonstrated no significant changes from pre-exposure values following exposures to either filtered air or WSP. The moderate exercise on the ergometer has a rare risk of causing leg cramps or soreness. The EKG patches cause a rare risk of skin irritation or blistering.

- b) Oral prednisone: Long-term use of prednisone is associated with a number of complications such as increased risk of infections, fluid and electrolyte disturbances, gastrointestinal complications, dermatoses, ocular complications (cataracts, glaucoma), adrenal suppression, increased risk of osteoporosis, myopathy, personality changes, insomnia, among other things. However, a single dose of prednisone, as proposed in this study, is associated with minimal side effects, and may only cause temporary euphoria or irritability, hunger, or insomnia. As the half-life of prednisone is 3-4 hours, these minor side effects will last no longer than 24 hours.
- c) Sputum induction: The saline solutions (3%, 4% and 5%) nebulized during sputum induction may cause throat irritation, but it is uncommon for the duration of discomfort to last more than a few minutes post procedure. The procedure also has a minimal risk of inducing bronchospasm, which is less of a concern in healthy adults.
- d) Spirometry: Potential risks include possible lightheadedness or wheezing.
- e) Mucociliary clearance scan: The radiation exposure from the MCC scan, including the Co57 transmission scan and the Americium 241 disks, which are used as fiducial markers, is approximately 177 mRems. This is less than the natural environmental radiation that adults receive every year, which in Chapel Hill is about 300 mRems.
- f) Exhaled breath condensate: There are no additional risks associated with the EBC procedure as study subjects are simply asked to exhale into a chilled tube.

- **Protections to Minimize Risk:**

- a) WSP exposure: Strict adherence to inclusion and exclusion criteria will be followed prior to subject enrollment, and medical history updated throughout study visits to affirm continued study eligibility. If participants develop any infectious processes during the washout period, period 2 will be delayed for a minimum of 4 weeks (as per exclusion criteria) following resolution of illness and/or completion of antibiotics. During WSP exposure, subjects will be monitored by direct observation or via closed-circuit television. Subjects will have EKG telemetry leads attached to monitor cardiac rate and rhythm during exercise throughout the exposure. Subjects will be aware that they can terminate their exposure for any reason and still receive compensation for their participation up to that point. A physician familiar with the protocol will be available for all challenge procedures. The investigator or duty physician will end the exposure if the subject is found to be suffering from any major adverse effect. An emergency “crash cart” with standard emergency medications, IV fluids, and a defibrillator are also readily available at the CEMALB in the unlikely event of a medical emergency during any challenge or study visit. Pulse oximetry will be performed during the exposures to wood smoke and filtered air, and the subject will be withdrawn from the chamber if the value is

<90%. The risk of discomfort associated with exercise will be limited because ability and response to exercise will be assessed at the training visit, and subjects with orthopedic issues that limit ability to pedal a bicycle will be excluded. Subjects will be encouraged to remain well hydrated to minimize risks from exercise. Should skin irritation develop from EKG patches, a topical steroid for symptomatic relief will be recommended.

- b) Oral prednisone: Dosing will be limited to a single dose with minimal side effects as noted above. In addition, those with hypersensitivity to prednisone will be excluded from the study as noted in Section 3.4.
- c) Sputum Induction: Throat irritation will be minimized by providing the subject with a drink (water, juice etc) and a snack after induction. An albuterol multidose inhaler will be immediately available in the event the subject experiences symptoms of bronchoconstriction; however as only healthy subjects are being enrolled in this study, no albuterol pre-treatment will be given. A physician on duty in the facility will be available during sputum inductions. If the covering physician feels that the subject's respiratory status is such that providing an induced sputum sample would place them at increased risk for significant bronchospasm, sputum sampling will be deferred. Baseline FEV1 and FVC will be measured before the start of the induction and at the end of each level (concentration) of saline inhalation. The FEV1 values that match a 10% and 20% reduction from baseline will be calculated and recorded. Subjects who have a 10-20% decrease in FEV1 after the 3% or 4% level of saline will not be advanced to a higher concentration of saline and will continue at the same level. If the FEV1 drops by > 20%, the induction will be stopped and the subject will be treated with 2 puffs of albuterol. Additional albuterol may be given if needed.
- d) Spirometry: Subjects will be seated in a non-rolling chair when spirometry is performed and standard methodology conforming to the ATS guidelines for measurement of spirometry will be used. Subjects will be instructed to notify the study staff if they feel lightheaded, and albuterol will be available in the event the subject experiences any unanticipated bronchoconstriction.
- e) Mucociliary Clearance: Radiation history is collected. Any subject who will exceed safe annual exposure limits will not be enrolled.
- f) EBC: Standard procedures are followed for EBC. No additional risk is present from an EBC.

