**4.7 Visit 5: Baseline (Period 2) (following a minimum 4 week washout)**

1. Review medical history and adverse events
2. Urine pregnancy test
3. Vital signs, oxygen saturation
4. Physical Exam

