## APPENDIX

a) Table of Study Procedures:

	V0 (Baseline)	V1 (Training)	V2 (post- MC)	Pre-WSP V3 (Prd 1) V7 (Prd 2)	Post-WSP V3 (Prd 1) V7 (Prd 2)	V4 (Prd 1) V8 (Prd 2)	V5 (Baseline- Prd 2)	V6 (post- MCC)	V9 (Completion visit)
Consent	X								
Review history/AE's	X			X	X	X	X		X
Vital Signs	X			X		X	X		X
Urine hCG (females only)	X	X		X			X		
Symptom Questionnaire				X	2X (post-WSP, hr post-WSP)	X			
Spirometry (FEV 1 )	X			X	X	X	X		
EBC				X	X	X			
Physical Exam	X			X		X	X		
Venipuncture				X	X	X	X		
Sputum Induction		X			X	X	X		
2 hour WSP chamber exposure				X					
MCC		X			X		X		
MCC Retention Scan			X			X		X	
Ergometric Cycle Train		X							
Prednisone vs placebo					X				

b) Symptom Questionnaire:

Please indicate if you are experiencing any of the symptoms or restrictions listed below, using the following scale to indicate the severity. Circle the number.

0 = NONE	(not present)
1 = TRACE/NOTICED	(barely detectable)
2 = MILD/LIGHT	(present, but not annoying)
3 = MODERATE	(present, but somewhat annoying)
4 = SEVERE/HEAVY	(present and very annoying and painful)

Symptoms	None	Trace	Mild	Moderate	Severe
1. Headache	0	1	2	3	4
2. Irritation of the Nose	0	1	2	3	4
3. Stuffy Nose/Sinus Congestion	0	1	2	3	4
4. Runny Nose	0	1	2	3	4
5. Dry or Sore Throat	0	1	2	3	4
6. Pain on Deep Inspiration	0	1	2	3	4
7. Unusual Fatigue	0	1	2	3	4
8. Eye Irritation	0	1	2	3	4
9. Shortness of Breath	0	1	2	3	4
10. Sneezing	0	1	2	3	4
11. Coughing	0	1	2	3	4
12. Wheezing/Whistling of Chest	0	1	2	3	4
13. Chest Tightness	0	1	2	3	4
14. Sweating	0	1	2	3	4
15. Other:	0	1	2	3	4

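### The Section 9 AE/SAE definition is narrower than the AE review planned elsewhere: it omits symptoms that fail no safety criterion and prompt no care, late care-seeking, and late-onset serious events

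*Combined protocol and SAP*

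**What the plan says.** The definition is in Section 9 of the combined protocol and SAP, and no other section gives a broader one.

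- **AE, route 1:** "An AE for a given volunteer will be defined as failure of any of the safety criteria outlined above". This route has no care-seeking condition and no 96-hour limit.
- **AE, route 2:** "Any symptoms that induce a volunteer to seek medical attention from any provider within 96 hours of a study visit".
- **SAE:** hospitalization, life-threatening or permanent illness or injury, "or death if these events occur within 96 hours of a study visit". A later event also counts if the clinical course leading to it "begins within 96 hours of a study treatment visit".

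Other parts of the document plan a wider collection:

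- Section 9 (monitoring procedures) has AEs reviewed and classified at every study visit, with the PI monitoring safety for the whole study.
- Section 4.7 lists "Review medical history and adverse events" at Visit 5, after a washout of at least 4 weeks.
- The appendix table has a row "Review history/AE's" marked at Visits 0, 3/7 (before and after exposure), 4/8, 5 and 9. The Section 4.5 procedure list for Visits 3 and 7 names no AE review.
- Sections 4.6 and 5.3 schedule a call for delayed AEs 3–7 days after Visit 4.
- The grading scale starts at "Grade 1 = Mild; asymptomatic or mild symptoms; clinical or diagnostic observations only; intervention not indicated".

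**The concern.** The definition decides what is recorded, graded and reported. AE reports to the IRB and DSMB, the 24–48 hour SAE report in Section 9, and the Section 4.13 rule that suspends the study for a study-related SAE all use these terms. If staff apply the definition as written, they would leave out:

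1. symptoms that fail no safety criterion and for which no care is sought, whatever their severity;
2. symptoms for which care is sought more than 96 hours from any visit;
3. serious events more than 96 hours from any visit whose course did not begin within 96 hours of a treatment visit.

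Staff who instead carry out an open AE review at Visit 5 would probably record more. Two people following the same protocol could therefore build different safety records.

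**Working it through.** **Symptoms without care-seeking.** The inputs are the Section 4.13 post-exposure criteria and the appendix questionnaire, which has 15 items scored 0–4. Two criteria rest on symptom scores alone. One is a total above 45 that does not improve to 15 or less within 6 hours. The other is a score above 3 for shortness of breath or cough at 24 hours.

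- Take a headache rated "4 = SEVERE/HEAVY" with every other item at 0. The total is 4, which is not above 45, and headache is neither shortness of breath nor cough. If no care is sought, neither AE route is met.
- Section 9 (potential risks) lists four expected effects of a single prednisone dose: euphoria, irritability, hunger and insomnia. None is among the 14 named items (15 less the open item for other symptoms). Written under the open item, any of them would still be an AE only by route 2 unless the total criterion were failed.

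**Days outside the 96-hour window (care-seeking and SAE routes only).** Section 9 does not say whether the window runs only after a visit or on both sides, so both readings are shown. 96 hours = 4 days. Only scheduled visits are counted. Section 3.3 gives 10 visits (Visits 0–9), so the call is not treated as a visit.

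*Visit 4 to Visit 5.* Visit 3 = day 0 and Visit 4 = day 1, so the window closes on day 1 + 4 = 5. The earliest Visit 5 is day 28 (washout counted from Visit 3) or day 29 (from Visit 4).

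| Earliest Visit 5 | Interval | Uncovered, after-visit window | Uncovered, two-sided window |
|---|---|---|---|
| Day 28 | 28 − 1 = 27 | 28 − 5 = 23 (85%) | (28 − 4) − 5 = 19 (70%) |
| Day 29 | 29 − 1 = 28 | 29 − 5 = 24 (86%) | (29 − 4) − 5 = 20 (71%) |

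*Visit 6 to Visit 7.* Reset Visit 5 = day 0. Visit 6 = day 1 (Section 4.8), and the window closes on day 5. Section 4.5 allows Visit 7 up to 6 weeks after Visit 5, which is day 42. The interval is 42 − 1 = 41 days. Uncovered: 42 − 5 = 37 (90%) or (42 − 4) − 5 = 33 (80%). These are maxima. Section 3.1 gives 4 weeks from Visit 0 and no figure from Visit 5. If 4 weeks applied here, the maximum would be 28 − 5 = 23 or (28 − 4) − 5 = 19 days.

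*Visit 8 to Visit 9.* Reset Visit 7 = day 0. Visit 8 = day 1, the window closes on day 5, and Visit 9 falls on days 5–10 (Section 4.9). Uncovered: 0 to 10 − 5 = 5 days, or at most (10 − 4) − 5 = 1 day two-sided.

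*Delayed-AE call.* Three to seven days after Visit 4 is days 4–8 after exposure, so at most 8 − 5 = 3 of the days it asks about are past the window. The synopsis counts 3–7 days from exposure, which gives 7 − 5 = 2.

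The mismatch is therefore large before Visits 5 and 7, and small for Visit 9 and the call.

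**The case against.** The case on the other side has real substance.

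- **Mandatory backstop.** A reader might infer that a late, related serious event would escape required oversight. It would not if it is an unanticipated problem. Section 9 requires such problems to be reported to the HRPO and reviewed by the RM, who reports independently to the IRB and DSMB. It also has the PI stop the research until they have assessed the report. None of this has a 96-hour limit. What remains is that the 24–48 hour SAE report and the study-related-SAE suspension rule would not apply.
- **Scope of the safety criteria.** Section 4.13 also has a pre-challenge list, which includes viral respiratory symptoms within 4 weeks and current allergic symptoms. If Section 9 means that list too, those symptoms count with no care sought and no 96-hour limit. Section 9 does not say. This rules out the reading that all symptoms without care-seeking are excluded, but it leaves out a headache or the listed prednisone effects.
- **Poor fit, not contradiction.** A review at Visit 5 can still pick up failed criteria, care sought within 96 hours of Visit 4, and serious events whose course began in time. The call and Grade 1 can also be reconciled with the definition, since a failed criterion may itself be mild.
- **Visit 7.** AE review there rests only on the appendix table, whose row combines history with AEs, and on the general statement in Section 9.
- **Severe multi-symptom cases.** Eleven items rated 4, none of them shortness of breath or cough, total 11 × 4 = 44 and fail no symptom criterion. But of the 13 other items, three (wheezing, chest tightness, pain on deep inspiration) trigger physician evaluation under Section 5.3 when scored above 3. Only 13 − 3 = 10 remain, so any such eleven include at least one of the three. Evaluation does not in itself make the event an AE, but it makes this example weaker than the single severe headache.
- **The 4-week washout.** It is time allotted for airway inflammation to resolve. The documents do not present it as an AE follow-up period, so it cannot show that the window should be 4 weeks.

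**Conclusion.** The concern holds in limited form. The Section 9 definition is narrower than the AE review, monitoring and grading planned elsewhere, and nothing in the documents widens it. Symptoms that fail no criterion and prompt no care are not AEs, even when severe. Care sought outside 96 hours is not an AE, and serious events with onset outside the stated windows are not SAEs.

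For the care-seeking and SAE routes, 70–86% of the days from Visit 4 to the earliest Visit 5 are uncovered, and at most 80–90% of those from Visit 6 to Visit 7. This rests on counting scheduled visits only. Unscheduled visits or contact with the study physician (Sections 4.10 and 5.3) could shorten the gaps if they count, which Section 9 does not state.

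A reader might take these percentages as a share of events missed. The documents give no event rate for these 14 healthy adults, so they do not support that. Suspension rules 1 and 2 in Section 4.13 use the individual criteria directly and are unaffected. Section 6 plans no analysis of AE counts, and no efficacy result depends on this point. It should be corrected because the safety record is otherwise ambiguous and the correction is cheap.

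**What to change.** Replace the Section 9 definition with one that agrees with Sections 4.6, 4.7, 4.13 and 5.3, the rest of Section 9 and the appendix table:

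- Record and grade untoward events found at the planned visits and the call as AEs, whether or not care is sought, through Visit 9.
- State which lists in Section 4.13 are meant by safety criteria, and whether the 96-hour window, if any part of it is kept, runs before a visit, after it, or both.
- State whether unscheduled visits and contact with the study physician count as study visits or care-seeking.
- Align the Section 4.5 list with the appendix table on AE review at Visits 3 and 7.
- Keep the individual withdrawal criteria as a separate list.

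A longer SAE period would widen what can trigger suspension for a study-related SAE. The sponsor must therefore reconcile that period with the Section 4.13 rule and say how the two work together. No change to the withdrawal or suspension rules is proposed here.

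The cost is protocol wording and somewhat more AE recording, including unrelated background illness. No visits or procedures are added.
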